**Monitoring Phase (Section 6.6)**

EVENT	Monitoring Phase ( $\pm 5$ days)	ET
Study days (D)/weeks (W)	Visits occur every 13 weeks starting from their entry into the Monitoring Phase (for up to 52 weeks or until Reversibility is met, whichever is sooner)	
Symptom-directed Physical Exam, as needed	X	X
Vital Signs a and Weight	X	X
Urinalysis a	X	X
Hematology and Chemistry a	X	X
Serum hsCRP	X	
LH, FSH, inhibin B, total Testosterone a collection time between 07:00-11:00 in the morning	X	X
Concomitant Medications	X	X
Assessment of Adverse Events b	X	X
Semen Collection c (2 samples as per collection instructions in Section 6.11)	X	X e
Date and time of most recent ejaculation d	X	

a As detailed in [Appendix 12](#).

b As detailed in [Section 7.3](#).

c Semen samples will be collected every 13 weeks from the day of study drug discontinuation, for up to 52 weeks or until Reversibility is met, whichever is achieved sooner. Reversibility is met when all sperm parameter(s) qualifying the subject to enter the Monitoring Phase return(s) to greater than 50% of Baseline (ie, to greater than [0.50 x Baseline]).

d This question will be asked prior to semen collection not at the site visit.

e Semen collection will be completed at ET visit only if previous semen samples were not collected within 2 weeks of ET.

**Extension Phase (Section 6.5)**

EVENT	Extension Phase ( $\pm 10$ days)	ET b	Safety follow-up
			30 Days after last dose of study drug ( $\pm 5$ days)
Study days (D)/weeks (W)	Week 26 up to 156 weeks a ( $\pm 10$ days)		
Symptom-directed Physical Exam, as needed	X	X	X
Vital Signs and Weight	X	X	X
TB QuantiFERON c	X		
Urinalysis d	X	X	X
Hematology and Chemistry d	X	X	X
Lipid profile (fasting) [Total cholesterol and subfractions] d,e	X		
Serum hsCRP	X		
LH, FSH, inhibin B, total Testosterone d collection time between 07:00-11:00 in the morning	X		
Concomitant Medications	X	X	X
Assessment of Adverse Events	X	X	X
Semen Collection (2 samples as per collection instructions in Section 6.11)	X	X i	
Date and time of most recent ejaculation f	X		
Study Drug Accountability g	X	X	
Study Drug Dispensation g	X		
12-lead ECG h	X	X	
PK collection (sparse)	X i		
HBV DNA j,k	X		
In-clinic dosing	X (Week 26)		

a Subjects in the Extension Phase (EP) will complete EP Week 26 visit and every 13 weeks thereafter up to 156 weeks.

Amendment 2

- b Any time a subject discontinues participation in the study prior to Week 156 in the Extension Phase, an Early Termination (ET) Visit is required.
- c In the EP subjects must have yearly QuantiFERON testing. Yearly TB testing begins 1 year from the screening TB test date. If yearly TB testing falls between study visits, the yearly TB testing should be performed at the visit prior to 1 year from the screening TB test date. Subjects with newly positive (converted) QuantiFERON® [or centrally reported equivalent assay] TB test should be discontinued from study drug. Subjects who were previously treated for TB with a complete and adequate course of therapy as per local Standard of Care and as verified by the investigator do not need to have yearly QuantiFERON® tests. Subjects previously treated for TB should be screened at least yearly for signs and symptoms consistent with reactivation of TB. Any subject with active TB should be discontinued from study.
- d As detailed in [Appendix 12](#). For visits that require fasting, subjects should not have any food or drink (except water) for at least 8 hours before the visit.
- e Lipid profile should be performed at Weeks 26, 39, 65, 91, 117 and 143.
- f This question will be asked prior to semen collection not at the site visit.
- g Only applicable for subjects on filgotinib.
- h ECG will be performed at Week 156 or ET (for subjects on open-label filgotinib only).
- i A sparse plasma PK sample is collected at Week 26 prior to study drug administration (for subjects on open label filgotinib only). Please refer to Section [6.14](#) for details on study drug administration.
- j An HIV-1/HIV-2 antigen/antibody test, a Hepatitis C virus antibody test, a Hepatitis B surface antigen, a Hepatitis B surface antibody and a Hepatitis core antibody test will be conducted on all subjects; Subjects with evidence of active Hepatitis B during the study, as evidenced by HBV DNA positivity, will be discontinued from study drug as outlined in the protocol.
- k Subjects with positive HBV core Ab and negative HBV DNA at Screening require ongoing monitoring with blood tests for HBV DNA every 3 months.
- l Semen collection will be completed at ET visit only if previous semen samples were not collected within 2 weeks of ET.

### **Appendix 3.66/68-joint Count (SJC66/TJC68)**

An overview of the joints to be assessed is provided below (subject's left and right):

- Temporomandibular
- Sternoclavicular
- Acromioclavicular
- Shoulder (\*)
- Elbow (\*)
- Wrist (\*)
- Metacarpophalangeal: first, second, third, fourth, fifth (\*)
- Proximal interphalangeal: first, second, third, fourth, fifth (\*)
- Distal interphalangeal: second, third, fourth, fifth
- Hip (assessed for tenderness only, not included in SJC)
- Knee (\*)
- Ankle
- Tarsus
- Metatarsophalangeal: first, second, third, fourth, fifth
- Proximal interphalangeal: first, second, third, fourth, fifth

Replaced (or otherwise not assessable) joints should be documented at Screening and omitted from further evaluation during the study. Parenteral corticosteroids are not routinely permitted during the study; if the subject requires a joint injection for AE of arthritis flare, the injected joint should be marked as "non-assessable" for the remainder of the study.

Joints flagged with an (\*) are used in the 28-joint counts (TJC28/SJC28).

[figure not shown]
Note: The TJC68/TJC28 and SJC66/SJC28 are used to derive the DAPSA and CDAI.

#### **Appendix 4. Physician's Global Assessment of Disease Activity (PhGADA)**

The PhGADA will be recorded on a 0-100 mm VAS, with 0 indicating “no disease activity” and 100 indicating “extreme disease activity” as relates to the subject’s arthritis. The evaluating physician and the subject should complete the global assessments independently of each other, as much as possible.

Instructions are provided below.

Considering all the ways arthritis affects your patient, draw a line on the scale for how well his or her condition is today.

[figure not shown]
Note: The VAS scale must be 100 mm long.

#### Appendix 5. Patient's Global Assessment of Disease Activity (PtGADA)

**In RA and PsA, the PtGADA will be recorded on a 0-100 mm VAS, with 0 indicating “very well” and 100 indicating “very poor”. The evaluating physician and the subject should complete the global assessments independently of each other.**

### Instructions:

Considering all the ways arthritis affects you, please draw a vertical mark (|) on the horizontal line below for how well you have been doing over the last week.

Note: The VAS scale must be 100 mm long.

Note: The PtGADA is part of the DAPSA and CDAL.

– Source: ASAS Handbook (Sieper, et al., 2009)

[figure not shown]
## Appendix 6. Patient's Global Assessment of Pain Intensity

### In PsA: (PPain)

The Patient's Global Assessment of Pain Intensity will be recorded on a 0-100 mm VAS, with 0 indicating "no pain" and 100 indicating "unbearable pain".

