While providing a treatment option for subjects with RA, PsA, AS and nrAxSpA, the present study seeks to evaluate the impact, if any, of filgotinib on spermatogenesis in humans. The observed effects of filgotinib on the testes are consistent across the nonclinical species tested, with observations of histopathological changes in testes and epididymides, together with reductions in sperm counts and reduced fertility in the rat. A mechanistic study in the rat suggested a reversible direct impact on the genes involved in cell cycle. A dose of 200 mg once daily of filgotinib results in an estimated mean clinical AUC of 2.8 µg·h/mL in subjects with RA, which represents an exposure margin of 2.3, 1.8, and 3.4-fold when considering the mean AUC in male dogs at the no observed effect levels (NOELs) in the 26-week and 39-week chronic toxicity studies, and 39-week targeted exposure toxicity study, respectively. The present study seeks to assess the impact of filgotinib at 200 mg, the highest proposed dose in the Phase 3 program, assessed by the proportion of male subjects who experience a ≥50% decrease in sperm concentration from Baseline when compared with placebo after 13 weeks of therapy. The proposed study design and subject population for GLPG0634-CL-227 have been selected to generate clinical safety data which would be broadly applicable to patient populations treated with filgotinib.

The present study has been designed in accordance with FDA Guidance for Industry: Testicular Toxicity: Evaluation During Drug Development (October 2018).

The study population will consist of males with active RA (defined as a CDAI score >10), active PsA (defined as DAPSA score >14) or active AS or nrAxSpA (defined as Bath Ankylosing Spondylitis Disease Activity [BASDAI] ≥4). Subjects must have demonstrated a prior treatment failure/intolerance to disease specific therapies but will be allowed to remain on permitted therapy, with the exception of SSZ which will be prohibited due to known risks of oligospermia and infertility {Pharmacia & Upjohn Co 2014}. Subjects will be stratified by Baseline sperm concentration and type of underlying rheumatic disease (RA or spondyloarthritis). In addition, subjects will also be stratified by use of MTX (yes or no) given its potential impact on

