### **4.2. Inclusion Criteria**

Subjects must meet all of the following inclusion criteria to be eligible for participation in this study.

- 1) Able to understand and willing to sign the informed consent as approved by the IRB/IEC. Written consent must be provided before initiating any Screening evaluations. Subjects must have read and understood the ICF, must fully understand the requirements of the study, and must be willing to comply with all study visits and assessments; subjects who cannot read or understand the ICF may not be enrolled in the study by a guardian or any other individual
- 2) Male between the ages of 21 and 65 (inclusive) on the day of signing informed consent

3) Body mass index (kg/m^2) of  $\geq 18.5$  to  $\leq 40$  at Screening, with no evidence of malnutrition as determined by the investigator

4) Diagnosis of RA, PsA, AS, or nrAxSpA for at least 12 weeks prior to Screening, meeting the corresponding specific classification criteria:

- RA, ACR/ European League Against Rheumatism (EULAR) 2010
- PsA, Classification criteria for Psoriatic Arthritis (CASPAR) criteria
- AS or nrAxSpA, Assessment of Spondyloarthritis International Society (ASAS) criteria for axial spondyloarthritis

5) For RA, PsA, AS, or nrAxSpA, meets the following criteria:

- RA
  - Inadequate response or intolerant to an  $\geq 12$ -weeks' course of csDMARD or bDMARD therapy for RA
  - Have an CDAI  $> 10$  at Screening
- PsA
  - Inadequate response or intolerant  $\geq 12$ -weeks' course of csDMARD or bDMARD therapy for PsA
  - Have a Disease Activity in Psoriatic Arthritis (DAPSA) score  $> 14$  at Screening
- Axial Spondyloarthritis (applicable to those with diagnosis of AS or nrAxSpA)
  - Inadequate response or intolerant to at least 2 NSAIDs, which may include cyclooxygenase-2 (COX-2 inhibitors) prescribed for a total period of  $\geq 4$  weeks OR to an at least 12-weeks' course of csDMARD or bDMARD therapy for spondyloarthritis
  - Have a BASDAI  $\geq 4$  at Screening
  - At Screening, subjects should have a high-sensitivity C-reactive protein (hsCRP)  $> 0.3$  mg/dL OR sacroiliitis according to the modified New York (NY) criteria OR a history of active inflammation on magnetic resonance imaging (MRI) consistent with sacroiliitis within 2 years of screening

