#### **6.19. Patient's Global Assessment of Pain Intensity (PPAIN) (used for DAPSA)**

For subjects with PsA, the patient's assessment of pain is a set of 2 questions on pain on the numerical rating scale.

The Patient's Global Assessment of Pain Intensity as related to arthritis will be recorded at the time points indicated in the Study Procedures Table ([Appendix 2](#)) and is provided in [Appendix 6](#).

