#### Instructions:

Please indicate with a vertical mark ( | ) through the horizontal line the most pain you had from your arthritis over the last week.

Note: the VAS scale must be 100 mm long.

Patient pain assessment will be used to calculate the DAPSA score:  $DAPSA = TJC68 + SJC66 + PtGADA (cm) + PPain (cm) + CRP (mg/dL)$ .

- Source: ASAS Handbook (Sieper, et al., 2009; Schoels, et al., 2010)

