5.2. Other Baseline Characteristics

Other baseline characteristics include:

- Body weight (in kg)
- Height (in cm)
- Body mass index (BMI; in kg/m²)
- Type of rheumatologic condition (RA, PsA, AS, nrAxSpA)
- Duration of inflammatory condition (in years)
- Physician's Global Assessment of Disease Activity (PhGADA) for all subjects
- Bath Ankylosing Spondylitis Disease Activity Index (BASDAI) for subjects with AS or nrAxSpA, continuous and for categories (< 4, \geq 4)
- Clinical Disease Activity Index (CDAI) for subject with RA, continuous and for categories (remission, low, moderate, and high) as described below
- Disease Activity in Psoriatic Arthritis (DAPSA) for subjects with PsA continuous and for categories (remission, low, moderate, and high) as described below
- High sensitivity C-Reactive Protein (hsCRP, mg/L)

- Smoking status (former, current, never)
- Alcohol Use — frequency of drinking in past 12 months (no alcohol in my life, no alcohol in past 12 months, 1 or 2 times in past year, 3-11 times in the past year, 1-3 times a month, < 4 times a week, ≥ 4 times a week)
- Alcoholic drinks per day consumed on a drinking day — past 12 months (1 drink, 2 drinks, 3-4 drinks, ≥ 5 drinks)
- Number of children fathered (0, 1-2, 3-4, ≥ 5)
- Prior use of csDMARDs (any including MTX)
- Concurrent MTX use status (yes, no) with subcategories for MTX dose (< 20 mg, ≥ 20 mg)
- Sperm concentration measured (15 to 25 M/mL, > 25 to 50 M/mL), > 50 M/mL)
- Sperm concentration (M/mL)
- Sperm total motility (%)
- Total sperm count (M/ejaculate)
- Ejaculate volume (mL)
- Sperm morphology (% normal) —WHO 1992 criteria
- Luteinizing Hormone (mIU/mL)
- Follicle-Stimulating Hormone (mIU/mL)
- Inhibin B (pg/mL)
- Total Testosterone (ng/dL)

Categories for CDAI (for RA) and DAPSA (for PsA) that will be summarized include:

Categories for Disease Activity	Clinical Disease Activity Index (CDAI for RA)	Disease Activity for Psoriatic Arthritis (DAPSA for PsA)
Remission	0 to 2.8	0 to 4
Low	2.9 to 10	5 to 14
Moderate	10.1 to 22.0	15 to 28
High	22.1 to 76.0	> 28

Duration of rheumatologic condition is calculated as:

$([\text{first dose date}] - [\text{date of initial diagnosis}] + 1 \text{ day}) / 365.25$

If the date of initial diagnosis is incomplete, then the following rules will be applied:

- missing day: use the first of the month
- missing month: use January

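### SAP 5.2 bands DAPSA in whole numbers although the score takes decimals, so eligible PsA scores above 14 and below 15 have no category; separately, the protocol describes the DAPSA pain item in two ways

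*Protocol*

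**What the plan says.** **Entry.** Protocol Section 1.3 sets the activity requirement as "active PsA (defined as DAPSA score >14", and inclusion criterion 5 in Section 4.2 applies the same cut-off at Screening.

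**Score.** Appendix 6 gives the only formula in the documents: "DAPSA = TJC68 + SJC66 + PtGADA (cm) + PPain (cm) + CRP (mg/dL" (closing bracket omitted here).

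**Categories.** SAP 5.2 lists "Disease Activity in Psoriatic Arthritis (DAPSA) for subjects with PsA continuous and for categories (remission, low, moderate, and high) as described below". The table beneath it gives remission 0 to 4, low 5 to 14, moderate 15 to 28 and high >28. The CDAI column of the same table has limits 0 to 2.8, 2.9 to 10, 10.1 to 22.0 and 22.1 to 76.0.

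**Pain item.** Protocol Section 6.19, whose heading assigns the item to DAPSA, says that "the patient's assessment of pain is a set of 2 questions on pain on the numerical rating scale", and then refers to Appendix 6 for the form. Appendix 6 instead says "Global Assessment of Pain Intensity will be recorded on a 0-100 mm VAS", asks for one mark showing the worst arthritis pain of the past week, and adds that "Patient pain assessment will be used to calculate the DAPSA score".

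**The concern.** A category scheme should cover every value the score can take, and at the least every value that the entry rule admits. Here the boundary between low and moderate activity sits on the entry threshold but leaves a hole one point wide just above it. A programmer working from the SAP must either leave such men unclassified or invent a rounding rule. Some rounding rules would show men admitted as having active disease as having low activity.

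The pain item raises a separate question of traceability. The two descriptions differ in scale type and in number of questions, and the score they feed decides PsA eligibility. A reader auditing eligibility cannot tell from the protocol alone which form was completed.

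**Working it through.** The plan states no figure to reproduce, because the bands are definitions. The check is whether they cover the score.

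**Inputs**
- Formula: Protocol Appendix 6, two whole-number joint counts plus two items in cm plus CRP in mg/dL.
- Resolution: Section 6.18 measures the patient global in mm on a 10-cm line, and Appendix 6 uses a 100-mm line for pain. Each therefore enters in 0.1 cm steps. CRP in mg/dL also takes decimals; criterion 5 itself uses an hsCRP cut of 0.3 mg/dL for axial disease.
- Entry rule: DAPSA >14.
- Bands: SAP 5.2, as listed above.
- Rounding rule for DAPSA: none found in the SAP. The no-rounding statement in SAP 6.1 concerns percentage change in sperm concentration.

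**Step 1: a score in the gap.** With illustrative values TJC68 3, SJC66 2, PtGADA 4.1, PPain 4.9 and CRP 0.4:

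3 + 2 + 4.1 + 4.9 + 0.4 = 14.4

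This exceeds 14, so the man meets the criterion. It is above 14 and below 15, so no band holds it.

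**Step 2: all scores from 0 to 39.9 in steps of 0.1.** Two runs have no band: 4.1 to 4.9 and 14.1 to 14.9. The first is below the entry threshold and matters little. Every score in the second is eligible.

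**Step 3: CDAI for comparison.** The same scan from 0 to 76.0 leaves no score unclassified. The CDAI limits abut at one decimal, and the edge between low and moderate matches the CDAI >10 entry rule.

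**Step 4: would rounding repair the existing bands?**

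| Eligible score | As written | Rounded down | Rounded half-up |
|---|---|---|---|
| 14.1 to 14.4 | none | Low | Low |
| 14.5 to 14.9 | none | Low | Moderate |

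Neither rule puts every eligible man in moderate or high.

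**Step 5: contiguous bands.** With ≤4, >4 to ≤14, >14 to ≤28 and >28, no score is unclassified and every score above 14 is moderate or high. Because these are inequalities, they also hold if CRP is reported to two decimals.

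**Step 6: the pain item, side by side.**

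| | Section 6.19 | Appendix 6 |
|---|---|---|
| Scale | Numerical rating, range not given | 100-mm VAS |
| Questions | Two | One |
| Route into DAPSA | Not stated | Entered in cm |

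Only the Appendix 6 version fits the formula directly. No arithmetic settles which form was used.

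**The case against.** The case against giving this weight is strong on consequence. DAPSA enters no primary or secondary endpoint, randomization stratum or model, and the Week 13 responder rule uses the physician's global assessment. SAP 5.2 also summarises DAPSA as a continuous variable, so a score of 14.4 is still reported. No testing of baseline characteristics is planned. The gap is less than one point wide, concerns PsA men only and may hold nobody. All of this stands, and it limits the finding to a descriptive table. It does not make the bands complete.

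On the pain item, Section 6.19 itself points to Appendix 6, which holds the patient instruction, the line and the only formula. DAPSA can be computed without ambiguity from that form. This also stands: what remains is a sentence in 6.19 that does not match the form it cites.

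A reader might infer that the same man can pass entry under Section 6.19 and fail under Appendix 6. The documents do not support that, because 6.19 contains no scoring rule under which to pass or fail. Suppose the other components total 9.5, the VAS reads 4.0 cm, and both numerical answers are 4 on an assumed 0 to 10 scale. Either answer, or their mean, gives 9.5 + 4 = 13.5, the same as the VAS. Crossing 14 would require adding the two answers, and nothing in the documents says to add them.

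**Conclusion.** The SAP 5.2 bands do not cover the score defined in Protocol Appendix 6. Scores above 14 and below 15 meet the PsA entry criterion but have no category, or become low if rounded down. The baseline category table may therefore not add up for PsA. Saying that it will fail goes too far: that needs at least one enrolled man in the range and no rounding rule added in programming, and the documents settle neither. The conclusion assumes that DAPSA is computed as written, from mm readings and CRP in mg/dL. Its effect is confined to a descriptive table.

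The mismatch between Section 6.19 and Appendix 6 is a genuine inconsistency of description. It shows no wrong eligibility decision. Nor can it be assumed that sites used the VAS form, although the cross-reference makes that likely.

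**What to change.** **SAP 5.2.** Replace the DAPSA bands with ≤4, >4 to ≤14, >14 to ≤28 and >28, so that the band edge equals the entry threshold. SAP Section 1 already provides for recording changes after finalization in the clinical study report. The cost is one table entry and the matching category derivation, with no new data and no effect on the primary analysis.

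**Protocol Section 6.19 and Appendix 6.** The sponsor should confirm which form produced the screening pain values, then reconcile the two passages with that fact. If numerical answers were used, state how the cm term was obtained from them. The confirmation should come before any rewording: Amendment 2 states that the study is already past the primary, secondary and exploratory analysis time points, and Appendix 2 schedules the pain item at Screening only. A new sentence in 6.19 therefore changes no past entry decision, and would misdescribe the data if it named the wrong form. The cost is one query and one wording change.

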#### Instructions:

Please indicate with a vertical mark ( | ) through the horizontal line the most pain you had from your arthritis over the last week.

Note: the VAS scale must be 100 mm long.

Patient pain assessment will be used to calculate the DAPSA score:  $DAPSA = TJC68 + SJC66 + PtGADA (cm) + PPain (cm) + CRP (mg/dL)$ .

- Source: ASAS Handbook (Sieper, et al., 2009; Schoels, et al., 2010)

## Appendix 7. Bath Ankylosing Spondylitis Disease Activity Index (BASDAI)

Please tick the box which represents your answer.

All questions refer to the last week.

## 1. FATIGUE

How would you describe the overall level of fatigue/tiredness you have experienced?

## 2 SPINAL PAIN

How would you describe the overall level of AS neck, back or hip pain you have had?

0	1	2	3	4	5	6	7	8	9	10
---	---	---	---	---	---	---	---	---	---	----

### 3. PERIPHERAL ARTHRITIS

How would you describe the overall level of pain/swelling in joints other than neck, back or hips you have had?

[figure not shown]
0	1	2	3	4	5	6	7	8	9	10
---	---	---	---	---	---	---	---	---	---	----

## 4 ENTHESITIS

How would you describe the overall level of discomfort you have had from any areas tender to touch or pressure?

[figure not shown]
